Statistical Methods:	Safety: The primary safety analyses will include incidence of DLTs by dose cohort. Safety analyses will summarize the incidence, grade and duration of toxicities according to the National Cancer Institute Common Terminology Criteria for AEs (NCI-CTCAE), version 4.03. All AEs will be listed and tabulated by system organ class, preferred term, and coded according to the Medical Dictionary for Regulatory Activities

	
(MedDRA). The incidence of AEs will be tabulated and reviewed for potential significance and clinical importance. Vital signs (including change in weight) and clinical laboratory test results will be listed and summarized descriptively by dose (for the dose escalation phase) and by tumor type (for the dose expansion phase). Any significant physical examination findings will be listed. ECG data will be evaluated by central review. Abnormalities, if present, will be listed. A separate listing and summary of all immune-related AEs (irAEs) will be provided.
 
Efficacy:
 
Efficacy assessments will be summarized separately for the dose escalation and dose expansion cohorts. In order to assess preliminary efficacy, the primary efficacy outcome measurement ORR, and the secondary efficacy outcomes, BOR, CBR, and TTR, will be tabulated by dose and tumor type. [REDACTED]
 
[REDACTED] Individual tumor measurements, tumor size and percent changes in tumor size will be listed. Changes in tumor size will be presented graphically for each specific tumor type. ORR and BOR will each be estimated based on the response evaluable population which is defined as subjects with measurable disease at baseline who receive the study drug and also have one post-baseline assessment of tumor response or are withdrawn due to progressive disease/death prior to first response assessment. DOR will be estimated for subjects who achieve complete response (CR) or partial response (PR). Other secondary efficacy analyses will be based on the all treated population and may be done for the response evaluable population as sensitivity analyses.
 
Pharmacokinetic parameters will be tabulated and summarized with descriptive statistics by dose level. Values for biomarker expression will be calculated at each observation time. Changes in expression from screening to each observation time will be assessed.

--	---

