**Table 1: Schedule of Visits and Procedures Dose Escalation (Phase 1) (Cont'd)**

Assessment Period	Screening	Cycle 1 and Cycle 2													Cycle 3 and Beyond			Post-treatment	
Study Days a	Day -28 to -1	Day 1	Day 2	Day 3	Day 4	Day 5	Day 6	Day 7	Day 8	Day 9	Day 10	Day 11	Day 15	Day 22b	Day 1	Day 8	Day 22 b	End of Treatment (+10 days)	Follow-up 3 mo
Administer fluids and advise patients aa		X	X	X	X	X									Days 1-5				
NKTR-214 administration bb		X													X				
Quarterly follow-up																			X

Footnotes:

- a. The acceptable visit window is + 1 days for Day 11 and ±1 day for Day 8 and Day 15 and ± 7 days for the follow-up visit post-treatment. Visits may be skipped or postponed if prospectively identified by the Investigator (e.g., national holidays, subject vacations). If Day 4 visit is missed then Day 4 assessments must be done at the next in-clinic visit. All procedures and examinations should be performed before the administration of study drug(s), except as indicated below.
- b. Assessments only applicable if dosing cycle is changed to 28-day cycle.
- c. The Institutional Review Board (IRB)-approved informed consent form (ICF) must be signed before any study-specific procedures or examinations are performed.
- d. An event occurring after the subject has provided informed consent, but before the first dose of study treatment, will be collected as medical history unless the event is either new and attributed to protocol-mandated procedures by the Investigator OR there is a significant change in the rate of occurrence or an increase in the severity of the pre-existing condition which is judged to be clinically important and attributed to the protocol-mandated procedures by the Investigator. Any new or clinically significant changes in the subject’s medical and/or cancer history that occur immediately after the first dose of drug will be recorded as AEs.
- e. Include prior cancer treatments: previous immunotherapy, chemotherapy, targeted therapy, radiation, OTC medications, herbs and dietary supplements.

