- f. Physical examinations at screening/baseline, at day 1 of each cycle, and at end of treatment should be complete assessments (evaluate all major organ systems, including the following categories: general, head, eyes, ears, mouth/throat, neck, heart, lungs, abdomen, lymph nodes, joints, extremities, integumentary, neurologic, and psychiatric). Other examinations may be focused, at the discretion of the Investigator, to identify changes from baseline or evaluate changes based on the subject’s clinical symptoms. Weight is to be reported at each visit, height at screening/baseline visit only.
- g. Assessments not applicable if dosing cycle is changed to 14-day cycle.

- h. Vital signs include temperature, pulse, respiration, systolic and diastolic blood pressure, and oxygen saturation. On dosing days, monitor the subject for 1 hour postdosing and record vital signs at the end of the hour. However, if the subject experienced a Grade  $\geq 2$  infusion-related reaction or hypotension during the study drug administration, the patient may be monitored for 24 hours per clinical judgment. Per clinical judgment, additional monitoring might be implemented for subsequent cycles.
- i. Vital signs will be assessed on days 6, 7, 9, and 10 of Cycles 1 and 2 either in-clinic or using home health care visits.
- j. A 5-minute summary ECG will be performed for all subjects at screening and during the 5 minutes prior to the time points of predose, 0.5 hr  $\pm$  5 min, 3 hr  $\pm$  10 min, 6 hr + 2 hr on Day 1 of Cycles 1 and 2 and on Days 2, 3, 4, 5, 8, 11, and 15 of Cycles 1 and 2. A 5-minute summary ECG starting 5 minutes before the predose timepoint will be performed on Days 1 and 8 of Cycle 3 and beyond, including End of Treatment (EOT). Frequency of ECGs may be increased if clinically indicated. Prior to performing ECGs, subjects should rest in the supine position for at least 5 minutes. All ECGs should be taken prior to the PK draw.
- k. Stress echocardiogram (either exercise or nuclear) will be performed for all subjects within 60 days prior to Cycle 1 Day 1 and at EOT to assess for cardiac function and left ventricular ejection fraction (LVEF). At the discretion of the Investigator, patients who are unable to perform a stress echocardiogram may instead have a multigated acquisition (MUGA) scan or transthoracic echocardiogram (TTE). The same assessment method should be used for the same subject throughout the study.

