- l. For women of childbearing potential, serum  $\beta$ -HCG pregnancy test is required at screening. Urine or serum pregnancy tests to be performed on Day 1 of each subsequent cycle and EOT. A pregnancy test does not need to be performed on women who are postmenopausal for at least 1 year or surgically sterile for at least 3 months before signing the ICF.
- m. Hematology performed at the indicated times by local laboratory: red blood cell (RBC) count, hemoglobin (Hgb), hematocrit (Hct), mean corpuscular volume (MCV), platelet count, white blood cell (WBC) count, and WBC differential (neutrophils, lymphocytes, monocytes, eosinophils, and basophils), mean corpuscular hemoglobin (MCH), mean corpuscular hemoglobin concentration (MCHC) ([Appendix 1](#)). If hematology demonstrates CTCAE grade 3/4 cytopenias, increase frequency to daily monitoring as clinically appropriate. Hematology assessments scheduled for the day of study drug dosing must be available and assessed for toxicity before dosing. The sampling for hematology assessment can be drawn up to 24 hours prior to dosing.
- n. Serum chemistry performed at the indicated times by local laboratory: sodium, potassium, calcium, chloride, creatinine, calculated creatinine clearance (Cockcroft-Gault), total bilirubin, albumin, alkaline phosphatase, CO2 or bicarbonate, lactate dehydrogenase (LDH), aspartate aminotransferase (AST), alanine aminotransferase (ALT), glucose, blood urea nitrogen (BUN), total protein (TP), gamma-glutamyl transferase (GGT), and uric acid ([Appendix 1](#)).
- o. Coagulation performed at the indicated times by local laboratory: partial thromboplastin time and prothrombin time ([Appendix 1](#)).
- p. Additional tests performed at Screening, on Day 15 of Cycle 1 and 2, and at End of Treatment: thyroid stimulating hormone, lipase, amylase, free thyroxine (T4), creatine kinase, HLA typing (only at screening) and on Day 1 beginning from Cycle 4 ([Appendix 1](#)).
- q. Microscopy is required only to follow-up clinically significant urine dipstick findings. List pH, specific gravity, protein, glucose, ketones, bilirubin, blood, and leukocyte esterase ([Appendix 1](#)).
- r. Serology tests include hepatitis B surface antigen (HBsAg), hepatitis C virus antibody (anti-HCV), and human immunodeficiency virus (HIV) antibody ([Appendix 1](#)).
- s. Unstained formalin-fixed, paraffin embedded, archival tumor tissue sections on slides are acceptable.

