## 5.0 SELECTION OF STUDY POPULATION

### 5.1 Inclusion Criteria

#### For Parts 1 and 2

1. Willing and able to provide written informed consent.
2. Histologically confirmed diagnosis of a locally advanced (not amenable to curative therapy such as surgical resection) or metastatic solid tumor.
3. Male or female patients, age 18 years or older at the time of signing the informed consent form (ICF)
4. Life expectancy >12 weeks.
5. Patients must not have received interleukin-2 [IL-2] therapy within 12 months of Cycle 1 Day 1.
6. Eastern Cooperative Oncology Group (ECOG) performance status 0 to 1.
7. Measurable disease per RECIST v1.1
8. Sample of archival tumor tissue and fresh baseline tumor biopsies (fresh baseline biopsy is defined as a biopsy specimen taken within 28 days prior to Cycle 1, Day 1) are required, except if inaccessible with Medical Monitor approval. Subjects must consent to allow acquisition of existing formalin-fixed paraffin-embedded (FFPE) material, either a block or unstained slides for performance of correlative studies.
9. Demonstrated adequate organ function, as defined below, within 14 days of treatment initiation:
  - a. WBC count  $\geq 2000/\mu\text{L}$  (after at least 7 days without growth factor support or transfusion)
  - b. Absolute neutrophil count (ANC)  $\geq 1500/\mu\text{L}$  (after at least 7 days without growth factor support or transfusion)
  - c. Platelet count  $\geq 100 \times 10^3/\mu\text{L}$  (transfusions allowed)
  - d. Hemoglobin  $\geq 9.0 \text{ g/dL}$  (transfusions allowed)
  - e. Serum creatinine  $\leq 2 \text{ mg/dL}$  (or glomerular filtration rate  $\geq 40 \text{ mL/min}$ )

- f. Aspartate aminotransferase (AST) and alanine transaminase (ALT)  $\leq 3X$  upper limit of normal (ULN)
  - g. Total bilirubin within normal limits unless associated with hepatobiliary metastases or Gilbert's syndrome, in that case total bilirubin  $\leq 2x$  ULN
10. On stress echocardiogram, documented left ventricular ejection fraction  $>45\%$  on cardiac stress test within 60 days prior to Cycle 1 Day 1. At the discretion of the Investigator, patients who are unable to perform a stress echocardiogram may instead have a multigated acquisition (MUGA) scan or transthoracic echocardiogram (TTE).
11. Oxygen saturation  $\geq 92\%$  on room air. NSCLC patients may use supplemental oxygen.

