### **6.3 Treatment Period**

Subjects who meet the selection criteria may start NKTR-214 treatment within 28 days following the Screening visit. The treatment period of the study is divided into multiple 21-day cycles with associated evaluations and procedures. Results of the assessments must be reviewed and documented before administering the first dose of the next cycle. No subject will be permitted escalation of dose level after assignment to a specific NKTR-214 dose level. Dose reductions after Cycle 1 due to AEs may occur following a discussion with the site Investigator and Medical Monitor. Every effort should be made to schedule visits within the protocol-specified windows.

For each dose level in Part 1, the first subject enrolled into a given dose cohort will be treated and monitored from Cycle 1, Day 1 through Cycle 1, Day 5 for safety and tolerability prior to dosing of additional subjects at that dose level.

Cycle 1, Day 1 will be the first day of treatment with NKTR-214 and Cycle 2, Day 1 will be the first day of the second dose of NKTR-214. Results from Day 1 laboratory evaluations must meet eligibility criteria prior to Cycle 1, Day 1 dosing.

During dose escalation, subjects who drop out prior to completion of Cycle 1 will be replaced unless the subject discontinued due to a DLT. During dose expansion, subjects will not be replaced.

Subjects will be treated until unacceptable toxicity, or disease progression per RECIST version 1.1. In the presence of disease progression, treatment may continue if there is clinical benefit as determined by the Investigator based on a reduction of symptoms related to cancer and absence of clinical deterioration or decline in ECOG performance status.

Note: Dosing may change to q14d or q28d following review and agreement by the Sponsor and Investigators. The change in cycle length will be determined by review of safety data and PK review of study drug.

After completing the pre-dosing procedures, administer NKTR-214 as an IV infusion over  $15 \pm 5$  minutes (Section 6.11).

Postdosing:

- The study site must be equipped for medical emergencies and have access to an intensive care unit.
- During dosing days, subject will stay in clinic for observation approximately 1 hour after dosing.
- Administer at least 2 liters of fluid (IV or self-administered orally [e.g., fluid containing electrolytes]) during Days 1 to 5 of every cycle.

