5 GENERAL ANALYSIS CONSIDERATIONS AND DEFINITIONS

The statistical analyses will be reported using summary tables, figures, and data listings. Unless otherwise specified, data collected during the dose escalation phase will be presented by dose cohort and overall. Data collected during the dose expansion phase will be presented by tumor type and overall.

Summary statistics for continuous variables will include the mean, standard deviation, median, minimum, and maximum. The mean will be presented to one decimal place beyond which the data were captured. The standard deviation will be presented to two decimal places beyond which the data were captured. The minimum and maximum will be presented to the precision with which the data were captured.

Categorical variables will be presented as frequency counts and percentages. A row or column denoted 'Missing' will be included in count tabulations where necessary to account for dropouts and missing values. Percentages will be rounded to 1 decimal place and the percent will be suppressed when the count is zero. The denominator will be the number of subjects in that dose cohort within the population of interest unless otherwise noted.

Time-to-event variables will be analyzed using the Kaplan-Meier method. The number and percentage of subjects with events or censored will be presented. The Kaplan-Meier estimates for quartiles (i.e., 25%, median, and 75%) and the 95% confidence interval for the median will be presented. All time to event variables will be plotted using the Kaplan-Meier method.

All data, including data collected from the electronic case report form (eCRF) and derived for statistical analysis, will be listed.

Cycle 1/Day 1 (C1D1) is defined as the first day of study treatment administration. Other study days will be calculated as follows:

- for any date post the date of C1D1:
Study day = visit date – date of C1D1 + 1
- for any date prior to the date of Cycle 1/Day 1:
Study day = visit date – date of C1D1

Unless otherwise specified, the baseline is defined as the last non-missing value prior to C1D1.

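### The SAP's baseline rule leaves out pre-dose Day 1 values, and its missing-stop-date rule turns open adverse events into completed durations (minor; descriptive safety summaries only)

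*SAP*

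**What the plan says.** **Baseline.** SAP section 5 gives the general rule: "Unless otherwise specified, the baseline is defined as the last non-missing value prior to C1D1". The same section says "Cycle 1/Day 1 (C1D1) is defined as the first day of study treatment administration". SAP sections 10.3 to 10.5 (laboratory, vital signs, ECG) use this baseline and give no other; none of them defines post-baseline.

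The protocol plans measurements on that day before the dose. Table 1 footnote a: "All procedures and examinations should be performed before the administration of study drug(s), except as indicated below". Table 1 footnote j schedules ECGs "at screening and during the 5 minutes prior to the time points of predose" and at later times. Section 6.3: "Results from Day 1 laboratory evaluations must meet eligibility criteria prior to Cycle 1, Day 1 dosing". Table 2 has matching visit and ECG footnotes for Part 2.

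**AE duration.** SAP section 6 sets a completely missing AE stop date to the date the subject discontinued from the study. SAP section 10.2 computes duration for each related TEAE as stop date minus start date plus 1, averages repeat episodes within a subject, and summarises by SOC and PT. It has no ongoing or censored category. Protocol 8.2 collects the outcome of each AE as its own item, and Protocol 8.5 provides outcome codes for events not resolved by 30 days after the last dose.

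**The concern.** Baseline for a safety change should be the last untreated value. Here the value taken closest to the dose is set aside for an older one, so whatever changed between screening and Day 1 is reported as change on treatment. The SAP also uses two boundaries within one safety analysis, because its TEAE definition divides at the first dose.

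On duration, the protocol expects some events to be unresolved when follow-up ends, so a blank stop date can be normal and not an error. Filling it with a study-exit date and treating it as resolution mixes censored times with completed ones. Duration of toxicity is a safety analysis named in the protocol synopsis, so this affects a planned output.

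**Working it through.** The plan gives no figure for either rule, so there is nothing to reproduce. The check is a reading of the text plus short algebra.

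**(a) Baseline**

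1. C1D1 is a day, not a dose time. SAP section 5 also counts study days from the date of C1D1. A value dated C1D1 is therefore not prior to C1D1, even if it was taken before the infusion.
2. Vital signs, ECG, hematology and chemistry are all scheduled on Day 1, before dosing. They are excluded unless taken on an earlier date. Hematology can escape: "The sampling for hematology assessment can be drawn up to 24 hours prior to dosing". Equivalent pre-dose samples are then kept or dropped by calendar date alone.
3. The fallback is screening, up to 28 days old. For the organ-function tests the limit is generally tighter: "Demonstrated adequate organ function, as defined below, within 14 days of treatment initiation".
4. Screening is not a stated reference for these measures. The synopsis names it for biomarkers: "Changes in expression from screening to each observation time will be assessed".
5. For one subject let S = screening value, P = pre-dose Day 1 value, Y = on-treatment value. Then Y − S = (Y − P) + (P − S). Averaging, mean(Y − S) = mean(Y − P) + d, where d is the mean drift from screening to Day 1. Drift enters every mean change one for one. If d = 0, expected mean changes are the same under either rule. The documents give no value for d.
6. Not affected: LVEF, the additional laboratory tests, tumor measurements and immunogenicity, none of which has a scheduled pre-dose C1D1 value.

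**(b) AE duration**

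1. Let A = start date, X = study-discontinuation date, F = last documented AE follow-up date. The SAP value is D = X − A + 1.
2. If the event is still ongoing at X, the true duration is at least D, so D is a lower bound analysed as complete. If AE follow-up stopped earlier, the data support only a duration of at least F − A + 1.
3. If the event resolved but its date was lost, the true duration is at most D, so D is an upper bound. The rule treats both cases alike although the recorded outcome separates them.
4. Effect on summaries, in assumed cases with D of at least 5 days:
   - Ten subjects, nine resolved in 5 days and one with D: mean = (45 + D)/10; median = 5 whatever D is.
   - Two subjects, one resolved in 5 days and one with D: median = (5 + D)/2.
   - One subject with episodes of 5, 5 and D: within-subject average = (10 + D)/3.

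   Each day added to X therefore adds 1/10, 1/2 or 1/3 of a day respectively.
5. X has no stated derivation. Protocol 5.3 speaks of withdrawal from the study for reasons such as progression, which puts X near the end of treatment. SAP 8.1 separates study from treatment discontinuation, and Protocol 4.1.4 continues survival contact for up to 3 years after C1D1, which can put X much later.
6. F is not settled either. Protocol 8.5 ends follow-up of ongoing AEs no later than 30 days after the last dose. Table 1 footnote w and Table 2 footnote v follow related AEs until they resolve or are judged chronic or stable. Protocol 5.3 follows attributable toxicities to resolution or permanent sequelae.

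**The case against.** The sponsor very likely meant 'before the first dose', and a programmer might code it that way. That may be so, but the SAP's own definition of C1D1 says otherwise, and one sentence settles it. It is also fair that the baseline choice is neutral for expected mean changes when there is no drift; this stands and limits part (a).

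A reader might infer that the rule inflates the share of subjects flagged for a QTc increase. The documents do not support that. It would require counting the pre-dose Day 1 ECG as a post-baseline record, which no section says, and a within-subject variability that is not given.

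A reader might also infer that AE durations will be overstated by hundreds of days. That does not follow either. For an event still open at study exit, a late date gives a less truncated lower bound, not an exaggeration; the fault is that it is not marked as censored. Only related TEAEs are summarised, and where these are followed to resolution, few stop dates should be completely missing. How many will be is unknown.

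Study discontinuation is a named disposition item in SAP 8.1, so the concept exists; only the derivation of its date is missing. Protocol 6.5 might be read as a further conflict over follow-up, but it asks only whether a related toxicity resolved or worsened and sets no period, so it does not contradict 8.5.

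Finally, all analyses are descriptive and all data are listed, so a reader of the listings could see the raw dates. This supports a low rating but does not make the summary tables right.

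**Conclusion.** Both points hold as minor defects in rules that the SAP states.

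Part (a) rests on the literal reading of C1D1 as a calendar day. It reaches change-from-baseline, CTCAE shift and QTc-change summaries for vital signs, ECG and laboratory values sampled on Day 1. Its size equals the unknown drift between screening and Day 1.

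Part (b) reaches the duration summary for related TEAEs with a completely missing stop date. Means and maxima are exposed most. Medians move when few subjects have the term, which is plausible because escalation cohorts can be as small as 3. The cases in the working show how sensitive each statistic is; they do not estimate bias.

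Nothing here alters ORR, DLT counts, or AE incidence or grade.

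**What to change.** **Baseline (SAP section 5).** Replace the rule with: 'Baseline is the last non-missing value before the first dose of NKTR-214, including C1D1 pre-dose assessments; post-baseline is any value after the first dose.'

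**AE duration (SAP sections 6 and 10.2).** Use the recorded AE outcome to separate two cases.

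- *Ongoing events:* flag and count them. Treat the duration as censored at the last documented AE follow-up date. Do not report it as completed or average it with completed episodes. Use Kaplan-Meier only where numbers suffice, and first join the records that Protocol 8.3 splits by severity level into single episodes, so that a grade change is not counted as resolution.
- *Resolved events with an unknown stop date:* query the date. If it stays unknown, leave the event out of the duration summary and report how many were left out.

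Keep the partial-date rules, and state how the study-discontinuation date is derived where they still use it.

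**Protocol.** Reconcile section 8.5 with Table 1 footnote w, Table 2 footnote v and section 5.3, so that the last AE follow-up date is defined.

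**Cost.** The SAP changes are wording and minor programming, with no new data for the AE part because outcome and dates are already collected. The protocol change is small in content, but if made by amendment it needs IRB/IEC review (Protocol 12.1 and 13.1). The SAP changes need not wait for it.
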